SAEs, whether related or not related to study drug, (including pregnancies) must be reported to Aegerion Pharmaceuticals on an SAE Report Form or similar form (e.g. CIOMS, MedWatch) and submitted as soon as possible but not more than 7 calendar days in the event of a death or a life-threatening event or in 15 calendar days for all other SAEs. SAE reports within 7 calendar days are to be transmitted via email:

SAE Email Address: [contact] and [contact]

If only limited information is initially available, follow-up reports are required. (Note: Follow-up SAE reports should include the same investigator term(s) initially reported). If an ongoing SAE changes in its intensity or relationship to study drug or if new information becomes available, a follow-up SAE report should be sent to the Aegerion Pharmaceuticals (or designee) using the same procedure used for transmitting the initial SAE report. All SAEs should be followed to resolution or stabilization.

Per NIH HRPP SOP 16, all serious adverse events will be reported to the NIDDK/NIAMS IRB at the time of annual review. The PI will report all deaths (that are not Unanticipated Problems) to the NIDDK CD and NIDDK/NIAMS IRB as soon as possible, but not more than 7 days after the PI first learns of the event, unless otherwise specified by the NIDDK CD and documented in the protocol.

Deaths

Per NIH HRPP SOP 16, the PI will report all deaths (that are not Unanticipated Problems) to the NIDDK Clinical Director and the NIDDK/NIAMS IRB as soon as possible, but not more than 7 days after the PI first learns of the event, unless otherwise specified by the NIDDK CD and documented in the protocol.

Rationale for Subject Selection

Subjects eligible for this study include mature adolescents and non-elderly adults with lipodystrophy. All subtypes of lipodystrophy (i.e. generalized, partial, acquired, and congenital) will be eligible. Although restricting the study to one or two lipodystrophy subtypes (such as the most severe forms: acquired and congenital generalized) would likely give greater homogeneity in the patient population, such restrictions would dramatically decrease feasibility in this extremely rare condition. Because each subject will be compared to him/herself in this within-subjects design, the effects of inter-subject heterogeneity will be less important.

For leptin-treated patients who are withdrawing from leptin, this study is of greater than minimal risk, and without prospect of direct benefit to subjects, but likely to yield generalizable knowledge about the subjects' condition, e.g. lipodystrophy. For those in the leptin naïve arm of the study, there is a prospect of direct benefit. Based on these criteria, mature adolescents ages 14-17 years will be permitted to participate in the leptin-naïve arm of the study. Even though there is the potential for clinical benefit, younger children and adults who are unable to give informed consent are unlikely to possess the emotional maturity to participate in such a complex and time-consuming study. Because the risk of pancreatitis with leptin withdrawal represents greater than a minor increment over minimal risk, children will not be enrolled in the leptin withdrawal arm of the study. As we gain more experience in risks of leptin withdrawal in adults, we may request NIDDK/NIAMS IRB permission to include children in this arm in the future. Adults over age 70 years are excluded in order to decrease inhomogeneity related to an aging population. Because there is no prospect for direct benefit, adults who are unable to give informed consent will not be eligible.

Withdrawal Criteria

1. **Withdrawal of consent.** A subject wishes to withdraw from the study as stated in the informed consent (all subjects reserve the right to withdraw from the study without prejudice).
2. **Adverse event.** A subject experiences an adverse event that in the investigator's opinion necessitates withdrawal from the study. Specific examples of adverse events that would result in withdrawal are:
 - a) Pancreatitis during the leptin withdrawal period in the leptin treated group. Pancreatitis is a clinical diagnosis, and will be suspected in the presence of moderate to severe abdominal pain accompanied by nausea and/or vomiting. If pancreatitis is suspected, amylase and lipase levels will be drawn, and GI consultation obtained. However, even if amylase and lipase levels are normal, in the presence of typical signs and symptoms of pancreatitis, leptin will be restarted.
 - b) Diabetic ketoacidosis during the leptin withdrawal period in the leptin treated group
3. **Investigator decision.** An investigator feels it is in the subject's best interest to terminate participation. The detailed reasoning behind this decision will be documented.
4. **Protocol violation.** Includes subject noncompliance, pregnancy, study entry criterion violation, or start of an unacceptable concomitant medication.

Subjects in the leptin treated group, who undergo leptin withdrawal during this study, will be immediately restarted on leptin if they withdraw from the study for one of the above reasons.

Risks/Benefits Analysis including Considerations of Alternatives to Participation

Benefits

1. **Leptin Initiation:** Leptin naïve subjects enrolled in this study will initiate leptin treatment under this treatment protocol. Since the patients included in this protocol have metabolic abnormalities, they have some likelihood of considerable clinical benefit from this trial. The potential benefits of leptin in lipodystrophy are discussed in detail in protocol 02-DK-0022. In brief, leptin has been shown to cause short-term improvements (within 14 days, the duration of the current protocol) in blood glucose and triglyceride levels³¹. Long-term benefits (over 3 years) of leptin in lipodystrophy have been demonstrated under protocol 02-DK-0022, and include decreased hemoglobin A1c, triglycerides, ALT and AST⁵¹. Given the clear benefits, in February 2014 the FDA approved leptin (Myalept) for treatment of individuals with generalized lipodystrophy. A review of the data obtained in 02-DK-0022 showed that leptin also leads to clinically important improvements in patients who have partial lipodystrophy with significant metabolic disease.
2. **Leptin Withdrawal:** Subjects undergoing leptin withdrawal as part of this study will not have any real or potential personal medical benefit accruing from study participation. However, they will contribute to important research that has the potential to improve medical treatment of lipodystrophy patients in the future.

Risks/Discomforts

1. **General:** Some patients may find the time needed to complete the research studies an inconvenience in their routine lives.

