This is a non-randomized, parallel group study. Two groups of patients aged 14 to 70 years with lipodystrophy will be studied: leptin naïve and leptin treated. Minors will only be included in the leptin naïve arm. All subjects will be stabilized on a weight maintenance diet for 5 days (Period 1). After this, leptin will be withdrawn from leptin treated subjects, and leptin will be initiated in leptin naïve subjects for a period of 14 days (Period 2). The same isocaloric diet will be continued throughout both Periods, permitting study of leptin's effects independent of energy intake.

All subjects will undergo metabolic testing on admission, at the end of Period 1, and throughout Period 2, to generate a detailed short-term time course of the effects of leptin initiation or withdrawal. At the end of Period 2, leptin will be continued in the leptin naïve subjects, and restarted in the leptin treated subjects. Repeat metabolic testing will be performed 6 months (ideally 5-9 months but may be extended to 12 months in foreign subjects) after leptin initiation in the leptin-naïve cohort to generate information on leptin's long-term effects.

Study Objectives

The primary aim of this study is to determine the energy intake-independent effects of leptin on energy metabolism in lipodystrophic subjects.

The null hypothesis is that, when caloric intake is fixed, leptin has no effects on energy metabolism.

The alternative hypothesis is that, when caloric intake is fixed, leptin does have measureable effects on energy metabolism.

The major aspects of energy metabolism to be studied are:

1. Lipid metabolism, including fasting lipids, lipolysis and fatty acid turnover, and ectopic lipid storage.
2. Glucose metabolism, including fasting glucose, endogenous glucose production, and insulin sensitivity
3. Energy expenditure, including total and resting energy expenditure, skeletal muscle work efficiency, and spontaneous physical activity

In addition, the effects of leptin on endocrine and autonomic function will be examined, including effects on the thyroid, gonadal, and adrenal axes, as well as blood pressure, body temperature, and heart rate.

Introduction

Leptin

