Exploratory outcomes for which we anticipate greater than 80% power include epinephrine and sympathetic nervous system tone. Discrepant data exist for the effects of leptin on thyroid function (specifically, T3) based on the model used (lipodystrophy versus 10% weight loss), and this study should help to clarify whether this effect does or does not exist in lipodystrophy. We do not anticipate observing significant changes in resting energy expenditure; however, because this procedure is minimal risk, we feel that it will be important to document negative results for this outcome. Certain outcome measures, such as liver triglyceride (for which liver size was a proxy in the table, above), and insulin sensitivity, appear to progressively change over time with leptin replacement. For these outcomes, a 2 week intervention may be insufficient to observe statistically significant results. For other outcome measures, such as intramyocellular triglyceride, preliminary data on the short-term effects of leptin are not available, but effects, if present, are unlikely to be detectable by two weeks.

Therefore, in addition to obtaining data after 2 weeks of leptin withdrawal or initiation, we will restudy subjects in the leptin-naïve group 6 months (range is 5-9 months) after leptin initiation to look for changes that may not be detectable by 2 weeks.

Because some subjects may not complete the study, or may not have interpretable data for each outcome, we plan to enroll up to 20 subjects in each group in order to have 10 completers per group.

Statistical Methods for Data Analysis

Data will be analyzed separately for the leptin naïve and leptin treated subjects. This is done because the effects of leptin withdrawal after long-term treatment are likely to be different from the effects of leptin initiation after long-term deficiency.

Analysis of Primary Outcomes

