Measurements in each of the primary outcomes will be analyzed using the paired t-test (for normally distributed variables) or Wilcoxon paired test (for skewed variables) to test if there is any significant difference between the two study periods (on and off leptin) for each group (leptin naïve and leptin treated), respectively. In addition, mixed models incorporating baseline (pre-diet) parameters as covariates will be used to adjust for any effects of the inpatient, metabolic diet, independent of leptin's effects. For variables with more than 2 measurements during Period 2, repeated measure linear models (Mixed model or GLM) will be used to study the time effect, using pooled data from the 2 periods. Potential covariates to be explored in the model include: Age, sex, race, percent body fat, lean mass, body weight, type of lipodystrophy, and endogenous leptin level. To account for any deviation from the isocaloric protocol diet, actual caloric intake will be included as a covariate in mixed model analyses.

Additional correlations between variables within and between each of the major outcome categories (glucose metabolism, lipid metabolism, and energy expenditure) will be analyzed using either Pearson's correlation or simple linear regressions. These include the following:

1. Association between change in total body insulin sensitivity and changes in hepatic insulin sensitivity, fasting plasma glucose, and C-peptide
2. Association between change in rate of lipolysis, and changes in fasting triglycerides and fatty acid turnover
3. Association between insulin sensitivity and ectopic lipid stores, and rates of lipolysis and fatty acid turnover
4. Association between change in total energy expenditure and changes in resting energy expenditure, skeletal muscle work efficiency, spontaneous physical activity, thyroid function, catecholamines, and cardiac autonomic nervous system tone.

Analysis of Secondary and Exploratory Outcomes

Methods for analysis of secondary outcomes will be similar to those for primary outcomes. In addition, we will perform analysis to study the following associations between categories of outcome measures:

1. Association between the Ectopic Lipid measurements with Glucose and Lipid measurements
2. Association between the Endocrine measurements with Energy Expenditure measurements

Analysis of long-term data

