Additional follow up data will be obtained and analyzed 6 to 12 months after leptin initiation for the leptin naïve patients. Long-term follow-up measurements for this group will be compared with the baseline using paired comparisons. Time-dependent effects will also be investigated using repeated measures analysis. The analysis methods to be used are similar to those used in the primary outcome analyses.

By Group Comparisons

Although most of the analyses will be performed separately for leptin naïve vs. leptin treated patients due to the consideration stated previously, exploratory analyses will be carried out to compare the two study groups. These analyses include:

1. Comparison of outcomes and baseline characteristics by group will be performed using t-test or rank test, depending on the distribution of measurement compared
2. Model analysis using general linear models will be performed by including group as a factor

Study Implementation

Subjects will be admitted to the Metabolic Research Unit in the NIH Clinical Center. They will remain as inpatients throughout the 19 day duration of the short-term portion of the study. After admission, they will undergo a history and physical examination, and baseline labs will be obtained. Baseline phenotyping will include measurement of resting energy expenditure, hemoglobin A1c, and fasting lipid panel, glucose, insulin, and C-peptide. Fasting triglycerides and hemoglobin A1c will be used to assess subject eligibility in the leptin treated group. Additional labs used to assess subject eligibility in all subjects include electrolytes, BUN, creatinine, CBC, and a pregnancy test for female patients of reproductive potential. Height, weight, blood pressure, resting pulse, temperature, and anthropometric data (e.g. skin fold measurements, waist circumference, etc.) will be obtained. Additionally, the clinical testing that was formerly included in 02-DK-0022 will be done: ECHO, OGTT, liver/abdominal and pelvic ultrasounds.

Diet

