12. Fasting research blood tests: Fasting glucose, insulin, C-peptide, markers of insulin action (e.g. IGFBP2), lipid panel, free fatty acids, and high-sensitivity C-reactive protein will be measured every other day. Markers of bone turnover (CTX and P1NP) will be obtained twice at the end of Period 1, twice at the end of Period 2, and during the follow-up visit for subjects in the leptin-naïve group. Additional blood samples will be stored for future analysis of leptin and inflammatory markers—as well as used to measure circulating RNA and DNA during periods in which patients do or do not receive leptin, to determine the effects of leptin on circulating nucleic acids and pharmacoepigenomics of leptin therapy.
13. Biochemical evaluation: A baseline biochemical evaluation, which includes: electrolytes, BUN, creatinine, LDH, CPK, SGOT, SGPT, bilirubin, alkaline phosphatase, calcium, magnesium, albumin, protein, iron, and transferrin, will be conducted during Period 1 and at follow-up.
14. Magnetic Resonance Imaging (MRI) and Magnetic Resonance Spectroscopy (MRS): Hepatic, muscle and central body fat will be measured by magnetic resonance imaging (MRI) and magnetic resonance spectroscopy (MRS). MR studies will be performed at the end of Period 1, at the end of Period 2, and during the follow-up visit for subjects in the leptin-naïve group. Studies are performed on a 3T MRI scanner using phased-array coils. B0 shim parameters are optimized with a breath hold B0 mapping method (1). Navigator gated T2 weighted (T2w) and breath-hold T1 weighted (T1w) images in coronal and axial orientations are used to prescribe a 20x20x20 mm³ spectroscopy volume in an area with high signal to noise ratio, free of obvious fatty structures or blood vessels. After additional manual shimming, and optimization of transmit power and WS RF level 32 signals are averaged with a minimum repetition time (TR) of 3s and 35 ms echo time (TE) with WET water suppression (WS) followed by 4 signals averaged with WS RF power set to zero. Spectral data are fitted with AMARES (2) using a model of four resonances for the lipid signals on the WS spectra. Additionally, the apparent T2's of the summed

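### Minors enter only the arm with the uncontrolled long-term comparison, so for LH pulsatility and bone turnover markers their maturation cannot be separated from a long-term leptin effect

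*Combined protocol and SAP*

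**What the plan says.** The Precis (Methods) restricts minors to one arm: "Minors will only be included in the leptin naïve arm". Rationale for Subject Selection repeats this: "mature adolescents ages 14-17 years will be permitted to participate in the leptin-naïve arm of the study". Neither section, nor the Inclusion Criteria, gives an expected number of minors, a cap or a pubertal stage.

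Only the leptin-naïve arm has a long-term visit. The Precis says: "Repeat metabolic testing will be performed 6 months (ideally 5-9 months but may be extended to 12 months in foreign subjects) after leptin initiation". Sample Size Justification gives the narrower window: "we will restudy subjects in the leptin-naïve group 6 months (range is 5-9 months) after leptin initiation".

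Under Analysis of long-term data, "Long-term follow-up measurements for this group will be compared with the baseline using paired comparisons", repeated-measures models are added, and "The analysis methods to be used are similar to those used in the primary outcome analyses". The covariates come from Analysis of Primary Outcomes: "Potential covariates to be explored in the model include: Age, sex, race, percent body fat, lean mass, body weight, type of lipodystrophy", with endogenous leptin level also listed.

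Bone markers are scheduled under Metabolic Testing, item 12: "Markers of bone turnover (CTX and P1NP) will be obtained twice at the end of Period 1". The same item repeats them at the end of Period 2 and at the follow-up visit. Endocrine Evaluation, item 1, repeats LH pulsatility at follow-up. Under Outcome Measures, both are additional outcomes, outside the three primary/secondary/exploratory families.

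**The concern.** In a before-after comparison without a control, any change over time is attributed to treatment. Over 14 days that matters little for maturation. Over 5 to 12 months in a 14- to 17-year-old, gonadotropin secretion and bone turnover may change without any drug. The plan places every minor in the one arm that has the long comparison, pools them with adults, and has no pubertal or growth term and no adults-only analysis.

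The design rationale, that each subject serves as his or her own control, deals with differences between subjects. It does not deal with change within a subject. The section Long-term follow-up names uncontrolled diet as a limit on these data but does not name maturation.

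What is at stake is the long-term estimate for two outcome groups. The Introduction says that leptin's effect on bone is little studied in humans, so even an exploratory estimate may be relied on.

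**Working it through.** The plan gives no figure to reproduce. Its power table covers the short-term comparison and has no row for LH or bone markers. The only inputs from the documents are n = 10 completers and alpha 0.05 (Sample Size Justification). The rest below is assumed.

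**1. Why an age main effect does not help.** Write the repeated-measures model as Y = a + b·age + c·time + error. The term b·age shifts a subject's level at both visits equally and cancels from the change. If m of n subjects have a maturational change δ and leptin does nothing, c estimates (m/n)·δ. Removing it needs an age-by-time term, or age in a model of the change score. The plan specifies neither.

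**2. Size of the shift, bone marker.** Assume no leptin effect, n = 10, m minors whose marker is k times the adult level, and a fall f = 15% in minors only. In units of the adult mean, the pooled baseline mean is (n - m + m·k)/n and the pooled change is -m·k·f/n. The ratio is

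shift = -m·k·f / (n - m + m·k)

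| m | k | Calculation | Shift |
|---|---|---|---|
| 2 | 3 | -0.90/14 | -6.4% |
| 2 | 5 | -1.50/18 | -8.3% |
| 3 | 3 | -1.35/16 | -8.4% |
| 3 | 5 | -2.25/22 | -10.2% |

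The adults-only change is 0 in every row. The multiple k has no source in the documents. With k = 1 the shift is -0.30/10 = -3.0% (m = 2) or -0.45/10 = -4.5% (m = 3). With no minors it is 0.

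**3. False-positive rate in the same setting.** Simulation, with adult log SD 0.3, measurement CV 10% and a two-sided 5% level:

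| m | k | Minors' share of absolute change | Paired t, raw scale | Wilcoxon |
|---|---|---|---|---|
| 2 | 3 | 50% | about 4% | about 7-8% |
| 2 | 5 | 61% | about 2% | about 7-8% |
| 3 | 3 | 63% | about 7% | about 12% |
| 3 | 5 | 74% | about 4% | about 12% |

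The few large changes in minors move the mean but also inflate the SD of the differences, so the t-test rarely rejects. On the log scale with the same 15% fall, the t-test rejects in about 7% (m = 2) and 10-11% (m = 3).

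**4. General scale, for LH or any marker.** Let minors drift by g SDs of the within-subject change. The bias in the mean is m·g/10 SD. Simulated two-sided paired-t rejection with no leptin effect:

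| g | m = 1 | m = 2 | m = 3 | m = 5 |
|---|---|---|---|---|
| 0.5 | 0.05 | 0.06 | 0.06 | 0.10 |
| 1 | 0.05 | 0.07 | 0.10 | 0.22 |
| 2 | 0.05 | 0.08 | 0.16 | 0.48 |

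With one or two minors the error rate barely moves, although the mean is shifted. Inflation becomes material with three or more minors and a drift of at least 1 SD.

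**The case against.** The strongest reply is that the documents only permit minors. There may be none, or few, at follow-up. Appendix D mentions 28 enrolled patients without ages. The marker multiple, the fall and the CV are all assumptions. This stands: a reader might infer that growth and puberty are being counted as leptin effects, but the documents support only that the two could not be told apart if minors are in the sample.

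A reader might also infer that the trial is likely to report falsely that leptin lowers bone turnover. With two or three minors the paired t-test stays at about 2-7%, and the Wilcoxon test, which the plan prescribes for skewed variables, reaches only about 12%. A median summary would also move less than the mean, by about -3% to -4%.

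It is tempting to add energy expenditure and lean mass. Metabolic Testing, item 4, normalises energy expenditure to DEXA fat-free mass, which is remeasured at follow-up, and lean mass, weight and age are candidate covariates. Growth in body size is therefore at least partly handled. Lean mass is not a listed outcome.

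Finally, the protocol already says that the long-term data do not answer the energy-intake question. That lowers the priority but does not remove the bias, since it presents the same data as evidence on the time course of leptin's actions.

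**Conclusion.** The point holds for LH pulsatility and bone turnover markers at the long-term visit only. The pooled, uncontrolled paired comparison cannot separate maturation in 14- to 17-year-olds from leptin, and no planned model term or sensitivity analysis does so.

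Under the assumed values the harm is a pooled bone-marker mean shifted by about -6% to -10% of baseline and a wider pooled error, rather than a likely false positive. The shift is smaller if minors' levels are closer to those of adults and zero if no minors enrol. For LH the documents support no numerical estimate.

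The 14-day primary comparison is essentially unaffected. This is a low-priority clarification.

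**What to change.** Add to Analysis of long-term data: *Long-term changes in LH pulsatility and in CTX and P1NP will be reported for all subjects and for subjects aged 18 or over at entry, with each minor's change listed. A long-term leptin effect on these outcomes will be claimed only if the adults-only estimate agrees with the pooled one.*

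Age at entry is the right cut, because the consent section foresees participants reaching 18 while on study. All other long-term outcomes can stay as planned.

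The cost is one extra table and a smaller, less precise sample for the adults-only estimate. No visit or measurement is added, and if no minors enrol the two estimates coincide.
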